If we observe differences in behavior and vigilance between groups, we will determine whether improvements in vigilance explain a significant portion of the improvement in behavior, using the steps to establish mediation outlined by Baron and Kenny⁸⁴, which consist of fitting a series of regression models and testing relations among variable corresponding to significance tests of the regression coefficients. Specifically, we will construct regression models with change from baseline to 12 month BRIEF2/P GEC score as the outcome, including a treatment indicator as an independent variable, with and without including the change in the Go-No-Go performance test as a covariate. We will compare the coefficients for the treatment indicator to examine how much of treatment effect on the BRIEF2/P is explained by changes in the GNG test. Point and interval estimates for the reduction in the coefficients will be provided. Similarly, if sleep duration (by actigraphy and parent report) and sleep-quality (by PSG and parent report) demonstrate treatment effects, we will explore these factors as potential mediators for changes in behavior and vigilance (if these outcomes show treatment effects).

Aim 2: For endpoints related to HCU (illness or injury requiring hospitalizations; emergency department visits; inpatient procedures; outpatient procedures; scheduled office visits; unscheduled office visit or urgent care visits; medication use), incidence rate per person will be calculated. Recognizing that these count data are likely to be non-normal and skewed, we will use Wilcoxon rank-sum tests to compare study groups. To better model the underlying distribution of the count data and take into account potential data dispersion and possible preponderance of zeros, we will use goodness of fit statistics (e.g., AIC/BIC), likelihood ratio tests or the Vuong test⁸² to choose among the zero-inflated negative binomial models, zero-inflated Poisson models or regular negative binomial models. The models that best fit the data will be used to model treatment effect adjusting for covariates. Incidence rate ratios comparing treatment groups will also be reported. We also will describe distributions of medication classes (e.g., antibiotics, nasal anti-inflammatory medications, asthma medications) and reasons for hospitalizations, etc. by group to identify reasons for HCU differences (e.g., infection; respiratory illness). Analyses will be performed both including and excluding events associated with the intervention (surgery and pre- and post-operative care, but not include the polysomnography).

Aim 3: Whether treatment effects pertain to some subgroups and not to others are of great clinical significance. Statistical tests of treatment by covariate interaction will be performed to assess whether treatment effect varies by age, baseline weight, atopy/asthma status, secondhand smoke, socioeconomic status, family functioning, baseline symptom severity (e.g., Sleep Disordered Breathing Scale) or race. Within the group of children with asthma, we will assess whether asthma exacerbations differ by treatment group, using similar approach for count data as described in the analysis for HCU indices.

If we identify race differences in treatment effects, we will explore whether those differences are explained by the measured social and environmental factors, such as measures of family functioning or secondhand smoke exposure. To address this question, we will use models similar to the mediated baseline by treatment interaction models proposed by Baron and Kenny⁸⁴ and MacKinnon⁸⁶, except that the mediators under consideration will be those measured social and environmental factors mentioned above. More specifically, we will fit the following models: (1) $Y = i_1 + c_1 X + c_2 Z + c_3 XZ + e_1$; (2) $Y = i_2 + c'_1 X + c'_2 Z + c'_3 XZ + bM + e_2$; (3) $M = i_3 + a_1 X + a_2 Z + a_3 XZ + e_3$, where Y denotes the outcome (e.g., BRIEF2/P GEC change score or GNG change score), X denotes the

treatment indicator, Z denotes race, and M denotes the potential mediator (measured social and environmental factor under consideration) for the racial differences in treatment effects (c_3). Our interest here is to explore the potential mediation effects corresponding to the effect of XZ to M to Y, through evaluating the significance tests for \hat{c}_3 , \hat{a}_3 , \hat{b} , and \hat{c}_3 (or $\hat{a}_3\hat{b}$), the estimates of corresponding regression coefficients.

One gap in the CHAT study was lack of objective data on nightly sleep duration, which may significantly influence behavior and cognition. In this study, we will evaluate whether baseline average nightly sleep duration and continuity obtained from in-home actigraphy are associated with: a) baseline behavior and performance measures; b) whether there is an interaction between sleep duration and treatment. Models will be similar to those described above. We also will evaluate whether changes in sleep duration and continuity are associated with changes in behavior and performance outcomes.

Impact of Coronavirus Disease 2019 (COVID-19) Pandemic

We will summarize data quality and missingness by whether the relevant visit (at baseline, 6 months, or 12 months) occurred (or was scheduled to occur) prior to or following 03/11/2020, the date on which the World Health Organization declared COVID-19 to be a global pandemic.

As a sensitivity analysis, we will examine the robustness of the co-primary efficacy analyses to the mid-trial onset of the COVID-19 pandemic. To do so, we will incorporate an indicator of pandemic onset as an additional covariate and consider its interaction with the visit and treatment group by visit interaction factors. Specifically:

Let B_{ij} be the j th recorded BRIEF GEC score for the i^{th} participant, let $X1$ and $X2$ be indicators of the 6-month and 12-month visit, respectively, and let $X3_i$ be an indicator of randomization to the eAT arm. Let C_{ij} be an indicator of whether the j th measurement for the i th participant was recorded following the onset of the COVID-19 pandemic (dated on 03/11/2020). We will fit the model

$$B_{ij} = \beta_0 + \beta_1 X1_{ij} + \beta_2 X2_{ij} + \beta_3 X1_{ij} * X3_i + \beta_4 X2_{ij} * X3_i + \beta_5 C_{ij} + \beta_6 X1_{ij} * C_{ij} + \beta_7 X2_{ij} * C_{ij} + \beta_8 X1_{ij} * X3_i * C_{ij} + \beta_9 X2_{ij} * X3_i * C_{ij} + b_i + \epsilon_{ij}$$

from which we will calculate the estimated mean baseline BRIEF GEC scores (or GNG sustained attention d' measures), as well as the changes in those scores from baseline to 6 months and from baseline to 12 months in each randomization arm, both before and during the COVID-19 pandemic:

- Estimated mean baseline score pre-pandemic: $\hat{\beta}_0$
- Estimated mean baseline score during the pandemic: $\hat{\beta}_0 + \hat{\beta}_5$
- Estimated mean change at 6 months (WWSC arm) pre-pandemic: $\hat{\beta}_1$
- Estimated mean change at 6 months (WWSC arm) during the pandemic: $\hat{\beta}_1 + \hat{\beta}_6$
- Estimated mean change at 12 months (WWSC arm) pre-pandemic: $\hat{\beta}_2$
- Estimated mean change at 12 months (WWSC arm) during the pandemic: $\hat{\beta}_2 + \hat{\beta}_7$
- Estimated mean change at 6 months (eAT arm) pre-pandemic: $\hat{\beta}_1 + \hat{\beta}_3$

- Estimated mean change at 6 months (eAT arm) during the pandemic: $(\hat{\beta}_1 + \hat{\beta}_6) + (\hat{\beta}_3 + \hat{\beta}_8)$
- Estimated mean change at 12 months (eAT arm) pre-pandemic: $\hat{\beta}_2 + \hat{\beta}_4$
- Estimated mean change at 12 months (eAT arm) during the pandemic: $(\hat{\beta}_2 + \hat{\beta}_7) + (\hat{\beta}_4 + \hat{\beta}_9)$

We will then assess the pandemic's impact on the randomized treatment effects by using standard methods to test the null hypothesis of $\beta_9 = 0$, and will assess its impact on children's BRIEF global composite scores (or GNG sustained attention d' measures) overall by testing the null hypothesis of $\beta_5 = \beta_6 = \beta_7 = \beta_8 = \beta_9 = 0$.

Data Quality Monitoring and Interim Monitoring

The study will be monitored routinely for issues of data quality, study conduct (including recruitment and follow-up rates), data quality and adverse events. Of particular concern will be attrition and cross-over rates which, if excessive, could jeopardize the integrity of the study. Monthly reports addressing these issues of study conduct, data quality and adverse events will be provided to the Steering Committee (aggregate data), and periodically to the DSMB and NIH. Given that the patient population consists of children who are otherwise healthy, who have mild SDB, and that the intervention is considered a standard clinical intervention, we do not anticipate that the interim analysis will yield efficacy data compelling enough to require early termination. However, we will propose to monitor the BRIEF2/P GEC score and GNG score, our primary outcomes, in planned interim analyses of efficacy and safety. We plan to perform one interim analysis after half of the study population has completed their 12-month evaluations. Based on our recruitment projections, most of the accrual will be complete at this time and therefore early stopping may not be relevant. To create a formal framework for assessment of interim results, the Haybittle-Peto boundary⁸⁵ will be used. That is, interim results for comparisons of the BRIEF2/P score and GNG score between treatment groups will be considered sufficient to consider early termination only if at least one of the between-group differences are statistically significant using a family-wide significance level of 0.001. The Haybittle-Peto stopping rule allows the final analysis to be evaluated at a 5% level of significance^{85;86}. Concurrence with the monitoring plan by the PI's, the DSMB and the NIH will be required prior to implementation of the plan.

Interim comparative data will be considered confidential and will be available only to the DSMB members and to the DCC statistician analyzing the interim data and preparing the DSMB report.

Statistical Software

The software of choice for most of the analyses will be SAS 9.4, which has a wide range of statistical methods, and provides the routines for the multiple linear regression as well all other statistical methods planned for this trial. Where necessary, SAS may be supplemented with procedures from other software packages such as STATA or R.

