Participants will undergo a standardized assessment of behavior, behavioral performance testing, and other health-related evaluations at baseline and 12 month follow-up time points. At 6 months caregivers will complete neurobehavioral assessments remotely. Virginia will have a 6 month visit in person and repeat baseline assessments. Participants will receive monthly check-in by telephone, , email and/or text messaging in order to maximize retention and to collect additional symptom and HCU reports. Text messaging will only be utilized with families who agree to receive text messages. After 12 months, children who did not get surgery who have a 12-month

PSG showing obstructive sleep apnea (apnea hypopnea index ≥ 3 /hr or obstructive index > 1 /hr) or whose parent reports ongoing symptoms/concerns will be referred back to ENT for further clinical management (such as adenotonsillectomy) as per standard clinical care.

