2.4.3. Follow-up Contacts

eAT arm only: AT surgery 1-4 weeks from randomization within Month 1

WWS arm only: ENT re-evaluation visit with 1-4 weeks after Endpoint Visit if indicated by 12-month PSG revealing obstructive sleep apnea (AHI ≥ 3.0 /hr. or obstructive apnea index > 1 /hr.) or parent reporting concerning symptoms.

Both groups:

- Monthly contact by telephone, email and/or text messaging , for health care utilization, medication, adverse event inquiries and to support study participation.
- Check In questionnaires and surveys will be completed bi-monthly, at months 2, 4, 6, 8, and 10.
- Interim remote visit at 6 months for caregiver questionnaires and neuro behavioral assessments, adverse event and health care utilization inquiry, and teacher forms of behavior rating scales.
 - Virginia will have in person child neurobehavior testing in addition to assessments above.
- Endpoint Visit at Month 12 for behavioral and performance testing; questionnaires; anthropometry, and BP measures. Behavioral rating scales mailed to teachers.
- Follow-up research PSG at Month 12
- Follow up questionnaires after participation ended to assess feasibility of conducting a study to evaluate long-term outcomes of mild SDB

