4.2. Inclusion Criteria

1. Ages 3.0 to 12.9 years at the time of screening
2. Diagnosed with MSDB defined as:
 - a. Parent report of habitual snoring that occurs most of the night on at least 3 nights per week, and has been present for at least 3 months (on average occurring > 3 nights per week or more than one-half the sleep time) *and*
 - b. Obstructive apnea index < 1/hr or obstructive apnea hypopnea index < 3 /hr and no desaturation < 90% in conjunction with obstructive events, confirmed on nocturnal, laboratory-based PSG

NOTE: Participants failing baseline screening PSG will be referred for clinical care.

3. Tonsillar hypertrophy ≥ 2 based on a standardized scale of 0-5
 - a. 0 = surgically absent
 - b. 1 = taking up < 25% of the space between the tonsillar pillars
 - c. 2 = taking up 25-50% of the space between the tonsillar pillars
 - d. 3 = taking up 51-75% of the space between the tonsillar pillars
 - e. 4 = taking up > 75% of the space between the tonsillar pillars
4. Deemed to be a candidate for AT by ENT evaluation, i.e., no technical issues that would be a contraindication for surgery such as submucous cleft palate.
5. Primary indication for AT is nocturnal obstructive symptoms (i.e., not recurrent infections or other indications)

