8.2. Participants Randomized to Watchful Waiting with Supportive Care

After 12 months, children who did not get surgery who have a 12-month PSG showing obstructive sleep apnea (apnea hypopnea index >or =3.0 /hr or obstructive index > 1/hr) or whose parent reports ongoing symptoms/concerns will be referred back to ENT for further clinical management (such as adenotonsillectomy) as per standard clinical care.

9. Study Procedures

A study visit schedule is provided in Appendix A. Visit time points, study procedures and assessments are listed in the order in which they occur.

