Following 12 months, participants in the WWS group will be referred to ENT for a clinical visit, if their 12-month PSG shows an AHI \geq 3 /hr or obstructive apnea index > 1/hr. or if the parent/caregiver reports concerns or symptoms. The 12-month end point was chosen to enable assessment of long-term therapeutic effects. However, data from the 6-month visit will be used to improve the study's statistical efficiency; help identify the time-course and trajectory of treatment response; and provide information for imputing missing 12-month data. In addition to the efficacy analyses described below, adverse events will be summarized and presented by treatment groups.

Aims, Hypotheses and Endpoints

Aim 1: To determine the effect of eAT on behavior, attention, SDB symptoms, sleep quality, and quality of life in children with MSDB.

Aim 2: To determine the effects of eAT on health care utilization (HCU) in children with MSDB.

Aim 3: To identify factors that moderate the response to AT, including age, asthma/atopy, obesity, secondhand smoke exposure, sleep duration, family functioning socioeconomic status, and race.

Endpoint for Primary Efficacy Hypotheses

The co-primary outcome of the randomized controlled trial will be the GEC Score from the BRIEF2/P and the GNG. Please see the CCC application for details on its reliability, responsiveness, and psychometric properties.

Primary Null Hypothesis

The primary null hypothesis is that the mean change at 12 months in the BRIEF2/P GEC Score and GNG sustained attention d' will be the same for children who were randomized to eAT or to WWS.

Secondary Null Hypotheses

- a) There will be no difference between treatment groups in the expected mean change at 12 months in other behavior/performance measures, SDB symptoms, and quality of life.
- b) There will be no difference between groups in expected HCU (illness or injury requiring hospitalizations; emergency department visits; inpatient procedures; outpatient procedures; scheduled office visits; unscheduled office visits or urgent care visits; medication use) during the 12-month study period.

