Aim 1: We will use the Wilcoxon rank-sum test to compare group changes in secondary behavior/performance measures including the GNG inhibitory control d'-prime and the average of the sustained attention d-prime and inhibitory control d-prime, SDB symptoms and quality of life endpoints over the 12-month study period. Generalized linear regression models will be used to model treatment effects adjusting for covariates. All outcomes other than PSG indices will be available at 6 months and 12 months and thereby can be analyzed using the mixed effects model outlined for the primary analysis, which does not assume a linear trajectory over time. For continuous outcomes which appear to have a linear trajectory over time, we will also estimate the rate of change in each treatment group and test the null hypothesis that the rates of change are equal for the eAT group and the WWS group using the following mixed effects model:

Let T denote time and $T=0, 1, 2$ refer to baseline, month 6 and month 12. Let X_3 denote the treatment indicator as before. The model will have each of the outcomes as response and include the main effects of T and the interaction effect of $T \times X_3$. The coefficient for $T \times X_3$ represents the treatment effect on linear trajectories.

Standard methods can be used to estimate this effect and test the null hypothesis of a zero effect.

For PSG indices (e.g., metrics of overnight hypoxemia, hypercapnia, sleep architecture, and breathing patterns) that are only available at baseline and 12 months, similar models can be used except that the variables corresponding to 6 months will be removed from the model. All participants enrolling in PATS entered the trial with an apnea-hypopnea index (AHI) under 3, i.e., without any evidence of obstructive sleep apnea syndrome (OSA). Estimating the proportion of participants who went on to develop OSA during the trial is thus of particular interest. We will also evaluate treatment effects on the proportion of participants with emergence of OSA (as defined by an $AHI \geq 3$) and 5 (indicating emergence of moderate or more severe OSA) at 12 months, and whether treatment effects differ by subgroups specified in Aim 3.

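### Emergent OSA at month 12 is defined on AHI alone, although the protocol calls a month-12 PSG OSA on AHI or the obstructive (apnea) index

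*Combined protocol and SAP*

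**What the plan says.** **Outcome.** Section 19, Secondary Analyses, Aim 1, singles out the proportion of children who develop OSA during the trial. It starts from the premise that "All participants enrolling in PATS entered the trial with an apnea-hypopnea index (AHI) under 3", which it equates with having no sign of OSA. It then plans to test treatment effects on "emergence of OSA (as defined by an $AHI \geq 3$) and 5 (indicating emergence of moderate or more severe OSA) at 12 months", and to see whether they vary across the Aim 3 subgroups. The obstructive apnea index does not appear in this definition.

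**Month-12 PSG elsewhere in the protocol.** Three sections attach the label OSA to a two-limb rule:
- Section 2.1: "PSG showing obstructive sleep apnea (apnea hypopnea index ≥ 3 /hr or obstructive index > 1 /hr"
- Section 2.4.3: "12-month PSG revealing obstructive sleep apnea (AHI ≥ 3.0 /hr. or obstructive apnea index > 1 /hr"
- Section 8.2: "PSG showing obstructive sleep apnea (apnea hypopnea index >or =3.0 /hr or obstructive index > 1/hr"

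The opening description in Section 19 repeats the thresholds as triggers for ENT referral (AHI at least 3, "or obstructive apnea index > 1/hr. or if the parent/caregiver reports concerns or symptoms"), without calling them OSA.

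**Entry.** Section 4.2 requires "Obstructive apnea index < 1/hr or obstructive apnea hypopnea index < 3 /hr and no desaturation < 90" percent with obstructive events. The Study Summary also joins the two indices with 'or', and lets AHI equal 3.0.

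**The concern.** The trial has two working meanings of OSA on the same month-12 recording. A child can be sent back to ENT because the PSG is described as showing OSA and then be reported in the results as not having developed it. No section explains why the outcome drops the apnea-index limb, and no sensitivity analysis restores it.

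The word emergence also needs a clean starting point. If the apnea index is ignored at entry, a case found on that index at month 12 cannot be called new without looking back at the baseline value.

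At stake is the reported rate of progression under watchful waiting and its comparison with surgery. Families and clinicians weighing observation will look for that figure.

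**Working it through.** **Plan's own figure.** There is none to reproduce: the documents give no expected proportion, sample size or power for emergent OSA. The only related input is the planned 12-month sample, 460 × 0.80 = 368, or 184 per arm.

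**Step 1: compare the rules.** OAI is obstructive apneas per hour. Assume AHI = OAI + hypopneas per hour, with no central or mixed events.

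| OAI | Hypopneas | AHI | Sections 2.1, 2.4.3, 8.2 (AHI ≥ 3 or OAI > 1) | SAP outcome (AHI ≥ 3) |
|---|---|---|---|---|
| 0.5 | 1.0 | 1.5 | no OSA | no OSA |
| 1.2 | 0.5 | 1.7 | OSA | no OSA |
| 2.0 | 0.5 | 2.5 | OSA | no OSA |
| 2.9 | 0 | 2.9 | OSA | no OSA |
| 0.5 | 2.5 | 3.0 | OSA | OSA |

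Every AHI ≥ 3 case satisfies the two-limb rule, so the rules differ only for children with OAI > 1 and AHI < 3. Relative to the protocol's wording, the AHI-only count is equal or lower, never higher.

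**Step 2: check the baseline premise.** Under the literal 'or' of Section 4.2, a child with OAI 2.0 and AHI 2.5 qualifies, because AHI is below 3. That child already meets the two-limb rule at entry. A child with OAI 1.0 and AHI 2.0 also qualifies through AHI, is not OSA under the month-12 rule (above 1), yet fails the entry limit on OAI (below 1). The two limits therefore differ at exactly 1.0. Under the Study Summary, AHI of exactly 3.0 is allowed; if unchanged at month 12 it would meet the SAP's cut for emergence.

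**Step 3: illustrate size (every rate is assumed).** Let pW and pE be the two-limb proportions in WWSC and eAT, and m the share of cases qualifying on OAI alone, taken as equal in both arms.
- Cases not counted = 184 × (pW + pE) × m
- AHI-only risk difference = (pW − pE) × (1 − m)
- Power, two-sided 5%, n = 184 per arm, with p1 = pW(1 − m), p2 = pE(1 − m), d = p1 − p2 and p̄ their mean: Φ{[d − 1.96√(2p̄(1 − p̄)/n)] / √[(p1(1 − p1) + p2(1 − p2))/n]}

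For pW = 15% and pE = 5%:

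| m | Not counted, of 368 | Risk difference | Power |
|---|---|---|---|
| 0 | 0 | 10.0 points | 0.90 |
| 5% | 1.8 | 9.5 | 0.88 |
| 10% | 3.7 | 9.0 | 0.86 |
| 20% | 7.4 | 8.0 | 0.81 |
| 30% | 11.0 | 7.0 | 0.75 |

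Across 10% vs 3%, 15% vs 5% and 20% vs 8%, with m from 5% to 30%, the number not counted runs from 184 × 0.13 × 0.05 = 1.2 to 184 × 0.28 × 0.30 = 15.5. With m = 0 nothing changes.

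The proportional shrinkage depends on m being equal in both arms. With m = 0 in WWSC and 30% in eAT, the difference would be 15 − 5 × 0.7 = 11.5 points, wider than 10. The undercount of cases has a known direction; the effect on the treatment comparison does not.

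**The case against.** The best defence is that the two-limb wording belongs to a referral rule for children who have not had surgery. The same rule also refers on parental concern alone, and a referral net may reasonably be wider than an analysis outcome. The SAP states its AHI definition openly and adds a second cut-off. The rule is the same in both arms, and scoring is central (Section 9.1.1) and blinded (Section 2.3), so the AHI ≥ 3 comparison is valid for what it measures. Section 19 treats analyses of secondary hypotheses as exploratory, and Section 3.2 does not list emergent OSA among the secondary endpoints. All of this stands, and it is why replacing the AHI outcome is not essential. It does not remove the mismatch: the referral passages are the only places where the protocol says what OSA on a month-12 PSG is, and they do so three times.

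A reader might infer more than the documents support:
- **That children with clear OSA by AHI could enter and be counted as new cases.** Sections 5.2 and 9.1.2 make children outside the AHI and desaturation criteria ineligible after central review, and Sections 6.2 and 10.4.3 exclude OSA. What remains is the loose 'or', AHI of exactly 3.0 in the Study Summary, and no firm entry limit on the apnea index: Sections 5.2 and 9.1.2 do not name that index, and Sections 6.2 and 10.4.3 do not define OSA.
- **That the SAP contradicts its own OSA label.** Its opening description gives the thresholds only as referral triggers.
- **That a known share of cases is missed, or that the arm comparison is biased.** No distribution is given, so any percentage only restates an assumption.

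**Conclusion.** The point holds as a definitional mismatch in an exploratory secondary outcome. Any child with obstructive apnea index above 1 and AHI below 3 at month 12 would be described as having OSA in the protocol and counted as OSA-free in the analysis, so the reported proportion can only be too low against the protocol's wording. The size is unknown. Under the assumed rates above it is about 1 to 16 of 368 children, and it is zero if no child qualifies on the apnea index alone.

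The premise that entry AHI below 3 means no OSA is likewise incomplete, because it leaves out the apnea index. The reading rests on taking the 'obstructive index' of Sections 2.1 and 8.2 to be the obstructive apnea index named in Section 2.4.3 and Section 19; the documents should use one term. The co-primary analyses are unaffected, and nothing here bears on which referral threshold is right.

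**What to change.** Reconcile the passages before any unblinded analysis, so that the definition cannot be chosen after seeing results. In the SAP:

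1. Define a two-limb emergent-OSA variable (AHI at least 3/hr or obstructive apnea index above 1/hr at month 12) among children below both limits on the centrally scored baseline PSG. State how an apnea index of exactly 1.0 and an AHI of exactly 3.0 are handled at baseline.
2. Make it the main definition, with the AHI cuts at 3 and 5 as supportive. Alternatively, keep AHI at least 3 with a stated reason and prespecify the two-limb version as a sensitivity analysis alongside both cuts.
3. Report by arm how many children qualify on the apnea index alone, at baseline and at month 12.
4. Restate the baseline premise to cover both indices. Align the 'or' and the AHI boundary between the Study Summary and Section 4.2 with what was applied at central review.

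The cost is one derived variable from PSGs that are already scored centrally, plus a short SAP edit. No new data and no change to care are needed.
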